### **4.2 Rationale**

#### 4.2.1 Rationale for the Trial and Selected Subject Population

Interestingly, the negative immune cell regulator, PD1 ligand-1 (PD-L1), has been found to be up-regulated on many tumors as mentioned above including HNSCC. Recently, Pembrolizumab was shown to have activity in metastatic HNSCC with a decrease in tumor burden in up to 46% of patients with recurrent and metastatic HNSCC (ASCO 2014) leading to the initiation of a phase III study in this group. Besides PD-L1 expression, it was shown that patients with low tumor burden had increased response rates to Pembrolizumab. Therefore, patients who have

had the bulk of their disease resected may have a superior response.

Additionally, [name] laboratory and others have demonstrated that MHC-1, PD-L1, and

[figure not shown]
preliminarily PD-L2 are further increased in response to radiation treatment suggesting a possible mechanism of resistance and that anti-PD-1 rather than anti-PD-L1 would result in less resistance. Importantly, 1 week pre-treatment with anti-PD-L1 antibody prior to radiation (but not 5 days post-radiation treatment) resulted in increased survival of mice bearing HNSCC tumors (see figure 2) compared to radiation alone. Additionally, others have

demonstrated that PD-L1 is also increased in response to Cisplatin exposure. Therefore, we hypothesize that *the addition of Pembrolizumab prior and concurrently to combined radiation or Cisplatin and radiation (CRT) after surgical resection in high risk HNSCC will result in enhanced tumor response.*

#### 4.2.2 Rationale for Dose Selection/Regimen/Modification

##### 4.2.2.1 Pembrolizumab

An open-label Phase I trial (Protocol 001) was conducted to evaluate the safety and clinical activity of single agent MK-3475. The dose escalation portion of this trial evaluated three dose levels, 1 mg/kg, 3

mg/kg, and 10 mg/kg, administered every 2 weeks (Q2W) in subjects with advanced solid tumors. All three dose levels were well tolerated and no dose-limiting toxicities were observed. This first in human study of MK-3475 showed evidence of target engagement and objective evidence of tumor size reduction at all dose levels (1 mg/kg, 3 mg/kg and 10 mg/kg Q2W). No MTD was identified.

PK data analysis of MK-3475 administered Q2W and Q3W showed slow systemic clearance, limited volume of distribution, and a long half-life. Pharmacodynamic data (IL-2 release assay) suggested that peripheral target engagement is durable (>21 days). This early PK and pharmacodynamic data provided scientific rationale for testing a Q2W and Q3W dosing schedule.

Similar efficacy and safety of Pembrolizumab was seen when dosed at either 2 mg/kg or 10 mg/kg Q3W in melanoma patients. In addition, there was a flat exposure-response relationship of Pembrolizumab for both efficacy and safety in the dose ranges of 2 mg/kg Q3W to 10 mg/kg Q3W which did not depend on tumor burden.

The choice of the 200 mg Q3W as an appropriate dose for the switch to fixed dosing is based on simulations performed using the population PK model of Pembrolizumab showing that the fixed dose of 200 mg every 3 weeks will provide exposures that 1) are optimally consistent with those obtained with the 2 mg/kg dose every 3 weeks, 2) will maintain individual patient exposures in the exposure range established in melanoma as associated with maximal efficacy response and 3) will maintain individual patients exposure in the exposure range established in melanoma that are well tolerated and safe.

A fixed dose regimen will simplify the dosing regimen to be more convenient for physicians and to reduce potential for dosing errors. A fixed dosing scheme will also reduce complexity in the logistical chain at treatment facilities and reduce wastage.

#### **4.2.2.2 Cisplatin**

Cisplatin is often given as either bolus dosing or weekly dosing when combined with radiation treatment in HNSCC. In locally advanced disease without surgical resection, patients are often offered bolus Cisplatin dosing at 100mg/m^2 days 1, 22 and 43 of radiation based off a pivotal study by Adelstein et al. The same dosing was used in the older adjuvant studies mentioned above but with a significant increase in toxicity over radiation alone especially in regards to increase in renal dysfunction, myelosuppression, ototoxicity and emetogenesis. In the post-operative setting, in which many patients have poor nutrition and decreased functional status, there is a concern that patients would not be able to tolerate this bolus dosing and other dosing schedules would be more ideal. Based on data from Ang et al. 2004, it was proposed that patients require at least a cumulative dose of 200mg/m^2 of Cisplatin regardless of the dosing schedule (fractionated, high dose, weekly). Weekly Cisplatin was also shown to be effective with concurrent radiation in nasopharyngeal cancer and was demonstrated to result in lower toxicity over the standard dosing, further strengthening a role for this dosing schedule in HNSCC. NRG has established weekly dosing to be the current standard for adjuvant studies and is currently being used in RTOG 1216 and 0920. Therefore, we feel weekly dosing (40mg/m^2 for 6 doses) is most appropriate in this patient population.

### 4.2.3 Rationale for Endpoints

#### 4.2.3.1 Safety Endpoints

Clinically, the addition of Pembrolizumab to Cisplatin and radiation has yet to be explored. Pre-clinically, the addition did not add any unexpected toxicity in small analyses. Based on the current safety profile of Pembrolizumab alone, and the fact that the toxicities are unique to immunotherapy compared to radiation and chemotherapy, we do not expect to observe any additional adverse effects and that this will therefore be a safe combination. However, because this combination has not yet been explored in this setting (although many clinical trials are currently being designed), we will continue to monitor safety throughout this study using CTCAE guidelines. We will perform a lead-in of 8 patients in each arm in order to determine any unexpected toxicities beyond what had been documented for these therapies. As long as current standard of therapy is not felt to be significantly impacted (delay in >2 out of 8 patients in each arm), the trial will proceed.

[figure not shown]
#### 4.2.3.2 Efficacy Endpoints

This is a phase II non-randomized study and therefore will rely on historical controls for the primary efficacy endpoint of disease free survival (DFS) in resected high risk HNSCC. Based on the pivotal RTOG 9501 and EORTC 22931 adjuvant studies, disease free survival at 1 year was approximately 66% and 76% respectively for the CRT arms and 58% and 72% respectively for radiation only arms (See table). The 3 year estimates are somewhat closer between the two studies.

Study Group	RTOG 9501		EORTC 22931	
	RT	CRT	RT	CRT
Disease Free Survival 1 year	58%	66%	72%	76%
Disease Free Survival 3 year	37%	47%	40%	57%

There were several differences in these studies including number of lymph nodes involved (94% had  $\geq 2$

lymph nodes in RTOG versus only 57% in EORTC) and the number of patients with at least 1 high risk feature (ECE or positive margins) was also different (approximately 70% of the patients in the EORTC and 59% of RTOG

18MAR2021

study) which may account for these differences.

Based on phase I data, Pembrolizumab resulted in response rates up to 46% at least in those patients positive for PD-L1. Therefore, we expect that the addition of Pembrolizumab will significantly reduce the chance of relapse in this population and therefore, will result in improved DFS. Most locoregional relapses (the most common cause of death in this group) occur within the first year. Therefore, our primary and secondary endpoints respectively will be DFS at 1 and 3 years, which will reflect early and late relapse. Our historical baseline will be based off the RTOG 9501 data due to the fact that entry criteria included either ECE, positive margins or  $\geq 2$  lymph nodes all of which are considered to be either high risk or high-intermediate risk which is the group we are most interested in for this study and encompasses our inclusion criteria.

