#### 5.1.2 Subject Inclusion Criteria

In order to be eligible for participation in this trial, the subject must:

1. Be willing and able to provide written informed consent for the trial.
2. Be  $\geq 18$  years of age on day of signing informed consent.
3. Patients who are eligible for resection must have one or more of the following clinical features:
  - a. Any T stage with  $\geq N2$  disease;
  - b. T4 disease, any N stage;
  - c. T3 Oral Cavity, any N stage; or
  - d. Clinical evidence of extra-capsular extension on scans.
4. Pre-operative scans including chest imaging preferably PET/CT and CT neck w/contrast. (CT chest and CT neck w/contrast would also be acceptable). If contrast is contraindicated, MRI neck is acceptable.
5. Must be willing to undergo definitive resection with neck dissection.
6. Be willing to provide tissue from a newly obtained core or excisional biopsy of a tumor lesion before study drug administration if unable to provide archived biopsy tissue. Please note sample does not have to be sent to UC prior to enrollment in study as long as it is documented that

sample exists prior to treatment. (For MDA only, patients with available archival tissue will also have a mandatory fresh biopsy at enrollment.)

7. Have a performance status of 0 or 1 on the ECOG Performance Scale.
8. Demonstrate adequate organ function as defined in Table 1. All screening labs should be performed within 10 days of treatment initiation.

Table 1 Adequate Organ Function Laboratory Values

System	Laboratory Value
Hematological	
Absolute neutrophil count (ANC)	$\geq 1,500 / \mu\text{L}$
Platelets	$\geq 100,000 / \mu\text{L}$
Hemoglobin	$\geq 9 \text{ g/dL}$ or $\geq 5.6 \text{ mmol/L}$ without transfusion or EPO dependency (within 7 days of the screening exam)
Renal	
Serum creatinine OR Measured or calculated a creatinine clearance (GFR can also be used in place of creatinine or CrCl)	within upper limit of normal (ULN) OR $\geq 60 \text{ mL/min}$ for subject with creatinine levels $>$ institutional ULN
Hepatic	
Serum total bilirubin	$\leq 1.5 \times \text{ULN}$ OR Direct bilirubin $\leq \text{ULN}$ for subjects with total bilirubin levels $> 1.5 \text{ ULN}$
AST (SGOT) and ALT (SGPT)	$\leq 2.5 \times \text{ULN}$
Albumin	$\geq 2.5 \text{ mg/dL}$
Coagulation	

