#### **5.3 Stratification**

After surgical resection, patients will be stratified into two groups: high risk patients with proven positive surgical margins or extracapsular extension of lymph nodes or intermediate risk including all patients not meeting criteria for high risk. There is a small chance that although patients are identified clinically to require radiation prior to surgery, that the pathology will deem the patient to be low risk and radiation would not be considered standard of care. In the event, the investigator feels it is not in the best interest of patient to administer radiation (or radiation would not be considered standard of care), then patient may be withdrawn from the study.

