### **8.2.4.2 Disease Free Survival**

Kaplan-Meier method will be used to estimate the disease free survival rates at 1, 3 and 5 years among patients treated with combined Pembrolizumab, radiation therapy and +/- Cisplatin. 95% CI of these rates will be provided. These survival rates at 1 year will be estimated and compared with historical data (RTOG 9501: 65.4% in CRT and 68.8% in RT) via the one-sample exact test, point and confidence interval estimation. We will also use the log-rank test and Cox model to compare the DFS between the trial data and the historical data if patient level data obtained from RTOG 9501. An interim analysis will be done throughout study at the PI and statistician discretion.

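### The RTOG 9501 criteria do not cover this trial's intermediate stratum, so the 68.8% benchmark is not matched to the patients tested against it

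*Combined protocol and SAP*

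**What the plan says.** Section 4.2.3.2 chooses RTOG 9501 because its "entry criteria included either ECE, positive margins or" at least 2 lymph nodes, "all of which are considered to be either high risk or high-intermediate risk", and adds that this is the population of interest and "encompasses our inclusion criteria".

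Section 5.1.2, item 3, requires one or more of four clinical features. One is N2 or higher. The other three set no nodal minimum: "T4 disease, any N stage", T3 oral cavity with any N stage, and clinical ECE on scans.

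Section 5.3 then defines the strata from pathology. High risk means positive margins or ECE. The rest are "intermediate risk including all patients not meeting criteria for high risk". The same section foresees a few patients whose pathology is low risk, and lets the investigator withdraw them without requiring it.

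Section 8.2.3.2 bases efficacy on everyone who received at least one pembrolizumab dose, grouped by stratum after resection. Section 8.2.4.2 compares 1-year DFS with "65.4% in CRT and 68.8% in RT" by a one-sample exact test. It adds a log-rank test and Cox model if RTOG patient-level data are obtained, and names no covariates.

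**The concern.** The trial has no concurrent control. Section 3.1 makes DFS in the intermediate stratum a primary objective, with improvement over historic data as its hypothesis, so the benchmark carries the whole inference for that stratum.

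A T4 patient with no positive nodes, clear margins and no ECE could not have entered RTOG 9501 on the criteria the protocol gives. Here that patient is eligible, goes into the intermediate stratum and is tested against the RTOG figure. If such patients do better than the RTOG intermediate group, DFS rises through case mix alone and could be read as a pembrolizumab effect. If they do worse, a real effect could be hidden.

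**Working it through.** **Who each population contains**

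| | RTOG 9501, as section 4.2.3.2 describes it | Intermediate stratum here (5.1.2, 5.3) |
|---|---|---|
| ECE or positive margins | excluded by the intermediate label | excluded |
| At least 2 nodes | required, as the only remaining entry route | not required |
| T4 or T3 oral cavity, 0-1 nodes | not eligible | included |
| Pathologically low risk | not eligible | included unless withdrawn |

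Nothing in 8.2.3.2 or 8.2.4.2 removes the last two rows from the comparison or adjusts for them.

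**Inputs.** Null 68.8%, alternative 88% and N = 40 are from section 8.1.3. One-sided alpha 0.025 with the one-sample exact test is stated there for the chemoradiation arm and is taken to apply to the radiation arm too.

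**The plan's own figure.** With X ~ Binomial(40, p), the critical value is the smallest r for which P(X ≥ r | p = 0.688) ≤ 0.025.
- P(X ≥ 33 | 0.688) = 0.0397, which is too large.
- P(X ≥ 34 | 0.688) = 0.0163, so r = 34 (85%).
- Power: P(X ≥ 34 | 0.88) = 0.802.

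This reproduces the stated power of over 80%. The planned arithmetic is sound; the question is the null.

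**False-positive rate if the true no-effect DFS is not 68.8%, keeping the rule of 34 of 40**

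| True no-effect 1-year DFS | P(X ≥ 34) |
|---|---|
| 70% | 2.4% |
| 72% | 4.3% |
| 75% | 9.6% |
| 78.2% (upper 95% limit of the benchmark, section 8.1.2) | 20% |

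The rate passes 2.5% just above 70%, less than 2 points above the benchmark.

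**Effect of case mix.** Let f be the share of the stratum with fewer than 2 nodes and g their 1-year DFS without a drug effect. The no-effect rate is p = (1 − f) × 0.688 + f × g. The documents give neither f nor g, so both are assumptions: f from 25% to 50%, g from 60% to 90%.

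| g | f = 25%: p, false-positive rate | f = 50%: p, false-positive rate |
|---|---|---|
| 60% | 66.6%, 0.8% | 64.4%, 0.4% |
| 65% | 67.9%, 1.2% | 66.9%, 0.9% |
| 75% | 70.4%, 2.7% | 71.9%, 4.2% |
| 80% | 71.6%, 3.8% | 74.4%, 8.3% |
| 85% | 72.9%, 5.5% | 76.9%, 15.1% |
| 90% | 74.1%, 7.7% | 79.4%, 25.5% |

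Example: f = 0.5 and g = 0.80 give 0.5 × 0.688 + 0.5 × 0.80 = 0.744, and P(X ≥ 34 | 0.744) = 0.083.

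**Power of a comparison restricted to at least 2 nodes** (null 68.8%, alternative 88%, alpha 0.025)
- 30 patients (f = 25%): rule 26 of 30, power 71%.
- 20 patients (f = 50%): rule 19 of 20, power 29%.

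**The case against.** A reader might infer that 68.8% describes a worse-prognosis group, so that the test is certainly too lenient. The documents do not support that. They give no DFS for T4 or T3 oral cavity patients with 0-1 nodes, and none by node count among patients without ECE or positive margins. T4 disease is itself advanced.

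The only nodal evidence is the contrast in 4.2.3.2: 94% had at least 2 "lymph nodes in RTOG versus only 57% in EORTC", with 1-year DFS in the radiation arms of 58% and 72%. That contrast is confounded. The arms mix risk groups, and EORTC had more patients with ECE or positive margins (about 70% against 59%). The gap between the radiation arms also shrinks to 37% against 40% at 3 years. A magnitude quoted only for favourable added patients would therefore mislead, because added-patient DFS of 60-65% takes the false-positive rate below the nominal 1.6%.

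Two further points stand in part. The subset behind 68.8% is labelled only as intermediate risk on radiation in 8.1.2, so its having at least 2 nodes throughout is an inference from the quoted entry criteria. And the plan has partial mitigation: the objective is framed as estimation, 8.1.2 also looks at the RTOG confidence interval, and a Cox model is possible. None of these deals with node count as written.

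What the objection leaves untouched is the contradiction between 4.2.3.2 and sections 5.1.2 and 5.3. The optional withdrawal does not resolve it, since 8.2.3.2 keeps every dosed patient.

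**Conclusion.** The sentence in 4.2.3.2 is wrong as written, and the 68.8% benchmark is not matched to the intermediate stratum. The direction of bias is not documented. A lenient test is plausible on the protocol's own terms, because it labels the RTOG patients high or high-intermediate risk while expecting some low-risk patients in this stratum.

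The size depends on two quantities that the plan does not give. Over the assumed ranges (25-50% with fewer than 2 nodes, 1-year DFS 60-90% in them), the false-positive rate runs from about 0.4% to 26%, against 1.6% as designed. The firmer statement is that the design has little room: 2.5% is passed once the no-effect DFS exceeds about 70%. This should be changed before analysis, but it does not show that a positive result would be false.

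**What to change.** 1. In 4.2.3.2, replace the claim of coverage with a statement that the RTOG 9501 criteria overlap with, but do not contain, this trial's criteria, and that intermediate patients with 0-1 nodes fall outside them.
2. In 8.2.4.2, pre-specify a supportive comparison with 68.8% restricted to intermediate patients with at least 2 pathologically positive nodes, reported beside the all-intermediate result. Do not require both to be significant.
3. Report how the conclusion changes with the null rate, for example at 68.8%, 72%, 75% and 78.2%. For reference, resetting the null at N = 40 gives power at 88% DFS of 65% at 72%, 47% at 75% and 28% at 78.2%.
4. If RTOG patient-level data are obtained, name nodal and T status as covariates in the Cox model.

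The cost is SAP wording. Neck dissection is already required, so node counts should be available from surgical pathology. Eligibility and sample size do not change.

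Two downsides should be stated in the plan. The subset has low power (about 71% with 30 patients, 29% with 20), so a non-significant result there is weak evidence. And nodes are counted after one pembrolizumab dose, so selecting on them conditions on something that treatment may have altered. Pre-operative clinical N stage should be reported alongside.

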#### 4.2.3.3 Biomarker Research

It has been established that the expression of PD-L1 on tumors and PD-1 on T cells in the microenvironment, confers a poor prognosis in HNSCC. In addition, the frequency of peripheral blood myeloid derived suppressor cells also strongly correlates with a poor prognosis. However, the inhibition of the PD-1/PD-L1 interaction results in impressive tumor responses in a variety of tumors. It is assumed that this is mediated through T-cell mediated tumor cell killing. However, the contribution of the microenvironment remains unclear. Additionally, analysis of tissue after inhibition of this response and the effect on the tumor microenvironment remains relatively unexplored. In this study, we have the unique opportunity to analyze resected tumor tissue after exposure to 1 dose of Pembrolizumab which will give insight to these processes. In addition, the mechanism of resistance to PD-1/PD-L1 inhibition is unclear. As mentioned in the background, up-regulation of PD-L2 may be an explanation for poor responses to PD-L1 inhibition but would not explain the lack of effect in at least 50% of patients to anti-PD-1. Here we will investigate possible novel mechanisms of resistance described in detail below.

##### Tumor Microenvironment and Mechanism of Resistance to anti-PD-1

The tumor microenvironment exerts an immune suppressive role in cancer by limiting the capacity of T cells to accumulate among cancer cells resulting in immune-mediated cell death. Various aspects of the tumor microenvironment have been shown to limit T cell function: hypoxia, indoleamine 2,3-dioxygenase (IDO), adenosine and PGE2. The suppressive effects of adenosine and hypoxia on T lymphocytes are mediated by ion channels (Kv1.3 and KCa3.1). Both adenosine and PGE2 signal through their respective receptors, cAMP/PKA and their effect in mast cells is mediated by KCa3.1 channels. Evidence exists that alterations of the tumor microenvironment improve the efficacy of

immune checkpoint blockade. In a recent study in mice, the combination therapy of anti-PD1 with blockers of the adenosine receptor (A2AR) proved to be superior to anti-PD1 monotherapy. On the other hand, the anti-PD1 therapy could also make the immune cells more sensitive to the tumor microenvironment as it has been reported that PD1 blockade in mice increases the expression of A2AR in tumor infiltrating T lymphocytes (TILs). The goal of this collateral study is to determine whether (1) the tumor microenvironment and tumor microenvironment-related features of TILs at baseline (pre-drug) can be used as predictors of responders and non-responders; (2) anti-PD-1 treatment alters the characteristics of TILs making them more susceptible to the immune suppression of the tumor microenvironment with the consequent development of resistance to anti-PD-1 therapy; (3) unique alterations of T cell phenotype and function pre-drug or after therapy can be found in peripheral blood T cells.

## 5.0 METHODOLOGY

### 5.1 Eligibility Criteria

#### 5.1.1 Diagnosis/Condition for Entry into the Trial

Histologically or cytologically confirmed locally advanced HNSCC including the oral cavity, larynx or pharynx (except nasopharynx).

#### 5.1.2 Subject Inclusion Criteria

In order to be eligible for participation in this trial, the subject must:

1. Be willing and able to provide written informed consent for the trial.
2. Be  $\geq 18$  years of age on day of signing informed consent.
3. Patients who are eligible for resection must have one or more of the following clinical features:
  - a. Any T stage with  $\geq N2$  disease;
  - b. T4 disease, any N stage;
  - c. T3 Oral Cavity, any N stage; or
  - d. Clinical evidence of extra-capsular extension on scans.
4. Pre-operative scans including chest imaging preferably PET/CT and CT neck w/contrast. (CT chest and CT neck w/contrast would also be acceptable). If contrast is contraindicated, MRI neck is acceptable.
5. Must be willing to undergo definitive resection with neck dissection.
6. Be willing to provide tissue from a newly obtained core or excisional biopsy of a tumor lesion before study drug administration if unable to provide archived biopsy tissue. Please note sample does not have to be sent to UC prior to enrollment in study as long as it is documented that

sample exists prior to treatment. (For MDA only, patients with available archival tissue will also have a mandatory fresh biopsy at enrollment.)

7. Have a performance status of 0 or 1 on the ECOG Performance Scale.
8. Demonstrate adequate organ function as defined in Table 1. All screening labs should be performed within 10 days of treatment initiation.

Table 1 Adequate Organ Function Laboratory Values

System	Laboratory Value
Hematological	
Absolute neutrophil count (ANC)	$\geq 1,500 / \mu\text{L}$
Platelets	$\geq 100,000 / \mu\text{L}$
Hemoglobin	$\geq 9 \text{ g/dL}$ or $\geq 5.6 \text{ mmol/L}$ without transfusion or EPO dependency (within 7 days of the screening exam)
Renal	
Serum creatinine OR Measured or calculated a creatinine clearance (GFR can also be used in place of creatinine or CrCl)	within upper limit of normal (ULN) OR $\geq 60 \text{ mL/min}$ for subject with creatinine levels $>$ institutional ULN
Hepatic	
Serum total bilirubin	$\leq 1.5 \times \text{ULN}$ OR Direct bilirubin $\leq \text{ULN}$ for subjects with total bilirubin levels $> 1.5 \text{ ULN}$
AST (SGOT) and ALT (SGPT)	$\leq 2.5 \times \text{ULN}$
Albumin	$\geq 2.5 \text{ mg/dL}$
Coagulation	
International Normalized Ratio (INR) or Prothrombin Time (PT)	$\leq 1.5 \times \text{ULN}$ unless subject is receiving anticoagulant therapy as long as PT or PTT is within therapeutic range of intended use of anticoagulants
Activated Partial Thromboplastin Time (aPTT)	$\leq 1.5 \times \text{ULN}$ unless subject is receiving anticoagulant therapy as long as PT or PTT is within therapeutic range of intended use of anticoagulants

aCreatinine clearance should be calculated per institutional standard.

9. Female subjects of childbearing potential should have a negative urine or serum pregnancy within 72 hours prior to receiving the first dose of study medication. If the urine test is positive or cannot be confirmed as negative, a serum pregnancy test will be required.

10. Female subjects of childbearing potential should be willing to use 2 methods of birth control or be surgically sterile, or abstain from heterosexual activity for the course of the study through 120 days after the last dose of study medication (Reference Section 5.7.2). Subjects of childbearing potential are those who have not been surgically sterilized, or have not been free from menses for > 1 year.
11. Male subjects should agree to use an adequate method of contraception starting with the first dose of study therapy through 120 days after the last dose of study therapy.

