#### 5.2.2.4.2 Cisplatin

Use the actual body weight for all patients. There should be no dose modifications because of obesity.

Cisplatin dose can be reduced up to 2 times if AEs occur (1st dose reduction of 25% to 30mg/m^2 and then subsequently to 23mg/m^2). However, if AEs as listed below continue to occur despite 2 subsequent dose reductions, therapy should be discontinued permanently. Chemotherapy dose should never be escalated.

Neutropenia: If on the day of scheduled treatment with Cisplatin the absolute neutrophil count (ANC) is < 1000/mm^3, hold chemotherapy treatment but not the radiation until ANC  $\geq$  1000/mm^3, then treat at 25% dose reduction. Neutropenic fever (i.e. any fever  $>$  38.5°C with an ANC <1000/mm^3) will require a 25% dose reduction of the next Cisplatin dose.

Thrombocytopenia: If on the day of scheduled treatment with Cisplatin the platelet count is < 75,000/mm^3, hold chemotherapy treatment but not the radiation until platelets are  $\geq$  75,000/mm^3, then treat at 75% dose.

Neurotoxicity: If grade 2 neurotoxicity develops, hold Cisplatin (but continue RT) until toxicity improves to < grade 1, then reduce the following Cisplatin dose by 25%. If any signs of grade 3 or greater neurotoxicity occur, discontinue Cisplatin, but continue RT.

Renal Adverse Events: Cisplatin dose should be based on the serum creatinine or creatinine clearance immediately prior to the second and third Cisplatin dose using the following guidelines:

Note: If creatinine is > 1.5 mg/dl, creatinine clearance must be calculated (Cockcroft-Gault) in order to make dose adjustment. If the calculated clearance is 50 mL/min or above, a 24-hour urine collection is not needed, but if the calculation is less than 50 mL/min, a 24-hour urine collection is mandated, and the Cisplatin dose will be determined as follows:

Serum Creatinine Creatinine Clearance Cisplatin Dose (Dose reductions should be made from current dose level)

$\leq$  1.5 mg/dl or > 50 ml/min then administer full dose

> 1.5 mg/dl and 40-50 ml/min then administer at 25% dose reduction

> 1.5 mg/dl and < 40 ml/min Hold drug\*

\*Cisplatin should be held (but the RT continued) and the creatinine measured weekly, until it is < 1.5 mg/dl or the creatinine clearance is > 50 ml/min, and then the next and following doses of Cisplatin should be given at a dose reduction of 25%.

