**Table 5 Laboratory Tests**

Hematology	Chemistry	Urinalysis	Other
Hematocrit	Albumin	Blood	Serum $\beta$ -human chorionic gonadotropin†
Hemoglobin	Alkaline phosphatase	Glucose	( $\beta$ -hCG)†
Platelet count	Alanine aminotransferase (ALT)	Protein	Total triiodothyronine (T3)
WBC (total and differential)	Aspartate aminotransferase (AST)	Specific gravity	Free tyroxine (T4)
Red Blood Cell Count	Lactate dehydrogenase (LDH)	Microscopic exam (if abnormal)	Thyroid stimulating hormone (TSH)
Absolute Neutrophil Count	Carbon Dioxide ‡	results are noted	
Absolute Lymphocyte Count	( $O_2$ or bicarbonate)	Urine pregnancy test †	Prothrombin time PT/INR

	Uric Acid		Partial Thromboplastin Time (PTT)
	Calcium		
	Chloride		Blood for correlative studies
	Glucose		
	Phosphorus		
	Potassium		
	Sodium		
	Creatinine		
	Magnesium		
	Total Bilirubin		
	Direct Bilirubin ( If total bilirubin is elevated above the upper limit of normal )		
	Total protein		
	Blood Urea Nitrogen		

† Perform on women of childbearing potential only. If urine pregnancy results cannot be confirmed as negative, a serum pregnancy test will be required.

‡ If considered standard of care in your region.

Laboratory tests for screening should be performed within 10 days prior to the first dose of treatment. After Cycle 1, pre-dose laboratory procedures can be conducted up to 72 hours prior to dosing. Results must be reviewed by the investigator or qualified designee and found to be acceptable prior to each dose of trial treatment.

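### The albumin entry limit in Table 1 is written in mg/dL, far below any plausible serum value, so as written it excludes no one; it appears to be a unit error with a probably small effect, confined to eligibility.

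*Combined protocol and SAP*

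**What the plan says.** Inclusion criterion 8 in section 5.1.2 requires each subject to "Demonstrate adequate organ function as defined in Table 1". Table 1 is therefore an entry condition, not background. Its hepatic block, next to the bilirubin and AST/ALT limits, contains the row "Albumin $\geq 2.5 \text{ mg/dL".

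The hematology block of the same table states hemoglobin as "\geq 9 \text{ g/dL}$ or $\geq 5.6 \text{ mmol/L}$ without transfusion or EPO dependency". The only footnote to Table 1 concerns how creatinine clearance is calculated.

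Albumin appears once more, in the chemistry column of Table 5 (section 7.1.3.1), in the row "Hematocrit Albumin Blood". That row runs across three columns and names the test only, with no unit and no limit.

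**The concern.** An entry limit works only if some patients could fall on the wrong side of it. A serum albumin limit in single milligrams per deciliter does not look like such a limit, because it lies orders of magnitude below the concentrations at which albumin circulates. The criterion would then be satisfied automatically.

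What is at stake is consistent eligibility. The literal text admits everyone. The same number read in g/dL would turn some patients away. For a patient between the two readings, eligibility depends on how the person checking Table 1 takes the unit. Section 8.1.4 names the lead center and six other sites, and section 10.6.2 has a monitor reviewing sub-site data, so several people will apply this row. A site that silently supplies g/dL departs from the written protocol. A site that follows the written protocol is left with a criterion that does nothing.

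**Working it through.** The plan derives no figure here that could be reproduced. The check is a unit conversion and a comparison.

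**Inputs**

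- Written limit: 2.5 mg/dL (section 5.1.2, Table 1).
- Conversion: 1 g/dL = 1,000 mg/dL.
- Range of serum albumin in patients: 1 to 5 g/dL. This is an assumption, because the documents give no reference range. It is set wide on purpose.

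**Step 1: convert the limit.** 2.5 mg/dL ÷ 1,000 = 0.0025 g/dL.

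**Step 2: compare the assumed values with the limit.** Ratio = (albumin in g/dL × 1,000) ÷ 2.5. The last column applies the same number in g/dL, only to show how far the result depends on the unit.

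| Assumed albumin (g/dL) | In mg/dL | Ratio to written limit | As written | If the unit were g/dL |
|---|---|---|---|---|
| 1.0 | 1,000 | 400 | passes | fails |
| 1.5 | 1,500 | 600 | passes | fails |
| 2.0 | 2,000 | 800 | passes | fails |
| 2.5 | 2,500 | 1,000 | passes | passes |
| 3.5 | 3,500 | 1,400 | passes | passes |
| 5.0 | 5,000 | 2,000 | passes | passes |

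**Step 3: sensitivity to the assumption.** A patient fails the written criterion only with albumin below 0.0025 g/dL. The bottom of the assumed range would have to be too high by a factor of 1.0 ÷ 0.0025 = 400 before anyone failed. The choice of range therefore changes the ratio but not the conclusion.

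**Step 4: look for anything that repairs the unit.** Table 5 gives neither unit nor limit, and the Table 1 footnote covers another test. Hemoglobin, also a blood protein, is in g/dL in the same table. The protocol uses mg/dL for creatinine in section 5.2.2.4.2 ("If creatinine is > 1.5 mg/dl, creatinine clearance must be calculated (Cockcroft-Gault) in order to make dose adjustment"), where 1.5 is a working threshold. The pattern fits a unit slip in the albumin row.

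**Step 5: trace what depends on it.** The power statement in section 8.1.3 and the analyses in section 8.2.4 do not use albumin. The effect stops at eligibility.

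**The case against.** The strongest reply is that the slip reveals itself. A coordinator with a laboratory report in g/dL would probably set it against 2.5 and take the unit as g/dL, as for hemoglobin a few rows above. Nothing in the documents suggests that anyone applies 0.0025 g/dL literally. Other safeguards also exist:

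- The UC PI confirms eligibility before the pre-surgical dose (section 5.2), which limits divergence between sites.
- Exclusion 11 lets the investigator exclude a patient for a laboratory abnormality.
- Entry also requires limits on performance status, bilirubin, transaminases and coagulation.
- Laboratory results must be reviewed and found acceptable before each dose (section 7.1.3.1).

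Most of this stands, and it limits the practical effect. It does not restore the criterion. Exclusion 11 is discretionary, and the UC PI confirms eligibility against the same table. None of these safeguards supplies a numeric albumin limit.

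Three stronger readings are tempting, and the documents support none of them.

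- A reader might infer that patients with low albumin have been enrolled. The documents hold no screening data, and they do not show how sites have applied the row.
- A reader might tie the limit to nutrition through section 4.2.2.2, which says "In the post-operative setting, in which many patients have poor nutrition and decreased functional status". That remark explains the preference for weekly over bolus cisplatin after surgery. The albumin limit is listed as hepatic and is checked within 10 days before the pre-surgical pembrolizumab dose. Nothing calls it a nutritional screen.
- A reader might say that the limit is 1,000 times below any value a patient can have. The factor is 1,000 only against 2.5 g/dL. Over the assumed range it runs from 400 to 2,000.

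**Conclusion.** The point holds as an apparent unit error in a binding entry criterion. As written, the albumin limit is 0.0025 g/dL, about 400 to 2,000 times below an assumed patient range of 1 to 5 g/dL, and it excludes no one. The size of the gap rests on that assumed range; the conclusion that no patient fails hardly does.

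This is a correction to the eligibility text. No design, power or analysis result changes. Many sites may already read the row as g/dL, so the number of patients affected is probably small, but the documents do not allow a count. They also do not show what limit was meant. That g/dL is the likely unit is an inference from the hemoglobin row, and the sponsor has to confirm it.

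**What to change.** 1. Check the albumin unit in Table 1 against the source document, to rule out a transcription fault.
2. Have the sponsor's medical lead confirm the intended unit and limit.
3. Correct the row by amendment or clarification letter, so that all sites and the monitor apply the same limit.
4. Check the screening albumin of patients already enrolled against the corrected limit. Albumin is part of the Table 5 panel, so this needs no new data collection.

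The cost is one table entry, a notice to sites and a short look-back. The downside is that some enrolled patients could prove to be outside the corrected limit and would need to be recorded as eligibility deviations. The efficacy population in section 8.2.3.2 is defined by receipt of at least one pembrolizumab dose, so such a finding would not by itself remove a patient from the primary analysis.
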